6.1 Pre-visit Restrictions

The following restrictions should be adhered to (for all study visits except where noted):

- Patients should refrain, when possible, from xanthine (chocolate, caffeine containing drinks and food), for at least 24 hours before and during visits. Decaffeinated beverages are permitted
- Patients should refrain from alcohol for 24 hours before and during visits (including visits for safety laboratory tests) and until all procedures for that study visit are completed
- Patients must fast (water permitted) from 2 hours pre-dose until 1 hour post-dose (does **not** apply to Screening)
- Patients should refrain from smoking at least 1 hour pre-dose, and at least 1 hour before any measurement of lung function
- Patients should refrain from strenuous exercise for 72 hours prior to visits and should undertake no unaccustomed strenuous exercise from Screening until the End of Study Visit

6.2 Screening

Written informed consent will be obtained by the Investigator as specified in Section 10.3 prior to any study related procedures being performed. This typically will need to be performed prior to the Screening visit to allow for discontinuation of any prohibited medications (see Section 5.8.1). Screening procedures may be performed over more than 1 day.

Patients will be screened to determine eligibility against the Inclusion and Exclusion Criteria between 7 and 14 days before the first dose of study treatment. Patients must observe the medication restrictions described in Section 5.8.1, and other restrictions described in Section 6.1. To account for diurnal variability in pulmonary function, the Screening visit is to take place in the morning.

The following assessments will be performed, generally in the order indicated (to the extent feasible):

- Obtain informed consent (if not done prior to Screening)
- Recording of demographic information, including height and weight
- Recording of medical/surgical and disease history
- Recording of prior medications and therapies; confirming that medications were withheld as required
- Vital signs
- Full physical examination (see Section 7.4.5)
- 12-lead ECG
- Reversibility test:
 - Pre-reversibility spirometry
 - Four puffs of albuterol
 - Post-reversibility spirometry (20 to 30 minutes after albuterol)

- Blood samples for laboratory screening and safety tests:
 - Viral serology
 - Follicle stimulating hormone (FSH; if required to confirm post-menopausal status)
 - Serum pregnancy (for women of childbearing potential only)
 - Hematology and blood chemistry
- Urinalysis
- Urine pregnancy (for women of childbearing potential only) – results should be obtained prior to the chest X-ray
- Chest X-ray (unless historical X-ray performed in last 12 months is available)
- Questioning for adverse events

If the patient meets all of the Inclusion and none of the Exclusion Criteria:

- Instruct patient to return in 7 to 14 days for Part A treatment

6.3 Part A: Single Dose Treatment

Patients must withhold all medications described in Section 5.8.1 prior to the treatment in accordance with the washout times provided. If not, the visit must be rescheduled so as to occur within the permitted windows. All restrictions defined in Section 6.1 should also be adhered to.

6.3.1 Pre-dose Assessments

The following assessments will be performed prior to dosing:

- Assess concomitant medications; confirm that medications were withheld as required, and that all eligibility criteria continue to be met
- Question for adverse events
- Weigh rescue medication canister
- Urine pregnancy test (women of childbearing potential only)
- 12-lead ECG
- Vital signs
- Brief physical examination (see Section 7.4.5)
- Spirometry; 1 hour (± 5 minutes) and immediately (within 5 minutes) pre-dose. **Note:** The average of the two pre-dose FEV₁ values must be within $\pm 20\%$ of the pre-albuterol value at Screening; otherwise, the patient will be screen failed in accordance with Inclusion Criterion #10
- PK sampling
- Inhalation training
- Assign randomization number from next in sequence available at the study center

6.3.2 Study Medication Administration

Patients will be dosed once with either blinded RPL554 or placebo according to the randomization scheme.

6.3.3 Post-dose Assessments

The following assessments will be performed, at the times indicated relative to the end of dosing:

- 12-lead ECGs at 1, 2, 4 and 8 hours (± 10 minutes)
- Vital signs at 1, 2, 4, 8, 12 and 24 hours (± 10 minutes)
- PK sampling at 15 (± 5) minutes, 30 (± 10) minutes and 1, 1.5, 2, 4, 8, 12 and 24 hours (the latter assessments all ± 15 minutes)
- Spirometry at 5 (± 2), 15 (± 5) and 30 (± 10) minutes and 1, 1.5, 2, 4, 8, 11.5, 12 and 24 hours (the latter assessments all ± 15 minutes)
- Weigh rescue medication canister again, if used during the visit
- Dispense new rescue medication after the 24 hour assessment
- Question for adverse events

Patients will be discharged from the study center after the 12-hour assessments and instructed to return the next morning; alternatively, they may remain resident at the study center overnight at Investigator discretion. Patients will be informed that they will be contacted at some point after discharge to schedule the first visit for Part B and to assess for any adverse events and concomitant medication use.

Early terminated patients should have an End of Study Visit, whether or not they participate in Part B.

6.4 Part B: Repeat Dose Treatment

Prior to each visit in Part B, patients must withhold all medications described in Section 5.8.1 in accordance with the washout times provided. If not, the visit must be rescheduled so as to occur within the permitted windows. All restrictions defined in Section 6.1 should also be adhered to. Study staff will call the patient the day prior to the start of Part B to remind patients of the following: to adhere to the medication restrictions above and, prior to the Day 7 visit only, 1) to take study drug that evening at the scheduled time and 2) **not** to take study drug the following morning prior to arriving at the clinic.

6.4.1 Day 1 of Each Treatment Period

6.4.1.1 *Pre-dose Assessments*

The following assessments will be performed prior to dosing:

- Assess concomitant medications and confirm that medications were withheld as required
- Counsel/remind patient of daily dosing schedule as needed
- Question for adverse events
- Dyspnea scale

- PK sampling
- Blood samples for laboratory safety tests (hematology and blood chemistry)
- Urine pregnancy test (women of childbearing potential only)
- Urinalysis
- 12-lead ECG
- Vital signs
- Brief physical examination (see Section 7.4.5)
- Spirometry; 1 hour (± 5 minutes) and immediately (within 5 minutes) pre-dose
- Inhalation training
- Dispense inhaler, study medication and rescue medication
- At Treatment Period 1 only, assign randomization number from next in sequence available at the study center

6.4.1.2 *Study Medication Administration*

Patients will be dosed once with either RPL554 or placebo according to the randomization scheme. The first two doses of study medication on Day 1 will be administered in the clinic. The second dose will be administered 12 hours (± 10 minutes) after the first dose

6.4.1.3 *Post-dose Assessments*

The following assessments will be performed, at the times indicated relative to dosing:

- Vital signs at 1, 2, 4, 8 and 12 hours (± 10 minutes)
- Dyspnea scale at 30 (± 10) minutes and 1, 1.5, 2, 4, 8 and 12 hours (the latter assessments all ± 15 minutes)
- PK sampling at 15 (± 10) and 30 (± 10) minutes and 1, 1.5, 2, 4, 8 and 12 hours (the latter assessments all ± 15 minutes)
- Spirometry at 5 (± 2), 15 (± 5) and 30 (± 10) minutes and 1, 1.5, 2, 4, 8 and 12 hours (the latter assessments all ± 15 minutes)
- Question for adverse events
- Weigh rescue medication canister
- Dispense study medication to patient

Patients will be discharged from the study center after the 12-hour assessments and instructed to return 6 days later for Day 7. Patients will be contacted by phone the night before the Day 7 visit to remind them to: 1) take their study medication in the evening of Day 6 and record the time, 2) withhold study medication prior to the visit the next day, 3) return their medication during the visit and 4) follow other medication and activity restrictions as described in Section 5.8.1 and 6.1.

6.4.2 Day 7 of Each Treatment Period

6.4.2.1 *Pre-dose Assessments*

The following assessments will be performed prior to dosing:

- Collect study medication
- Weigh rescue medication canister
- Assess study medication compliance (see Section 5.10);
- Assess concomitant medications; confirm that medications were withheld as required and record time of prior evening dose of study drug
- Question for adverse events
- Dyspnea scale
- PK sampling
- Blood samples for laboratory safety tests (hematology and blood chemistry)
- 12-lead ECG
- Vital signs
- Brief physical examination (see Section 7.4.5)
- Spirometry; 1 hour (± 5 minutes) and immediately(within 5 minutes) pre-dose

6.4.2.2 *Study Medication Administration*

Patients will be dosed once with either RPL554 or placebo according to the randomization scheme.

6.4.2.3 *Post-dose Assessments*

The following assessments will be performed, at the times indicated relative to dosing:

- Vital signs at 1, 2, 4, 8 and 12 hours (± 10 minutes)
- Dyspnea scale at 30 (± 10) minutes and 1, 1.5, 2, 4, 8, 11 and 12 hours (the latter assessments all ± 15 minutes)
- PK sampling at 30 (± 10) minutes and 1, 1.5, 2, 4, 8 and 12 hours (the latter assessments all ± 15 minutes)
- Spirometry at 30 minutes (± 10) and 1, 1.5, 2, 4, 8, 11 and 12 hours (the latter assessments all ± 15 minutes)
- Question for adverse events

Patients will be discharged from the study center after the 12-hour assessments and instructed to return as follows: 1) for all but the final treatment period, 7 to 10 days later for Day 1 of the next treatment period, 2) for the final treatment period, 4 to 10 days later for the End of Study visit.

6.5 End of Study Visit

All completed and early terminated patients should complete the End of Study visit. The following will be performed:

- Assess concomitant medications
- Full physical examination
- Vital signs
- Blood samples for laboratory safety tests (hematology and blood chemistry)
- Urinalysis
- Urine pregnancy test (women of childbearing potential only)
- Spirometry
- Question for adverse events

7 STUDY METHODOLOGY

7.1 Demographics, Baseline Characteristics and Eligibility Assessments

Safety assessments (laboratory safety tests, vital signs, 12-lead ECG and physical examination) will be performed at Screening as part of the eligibility assessment as described in Section 7.4.3 to 7.4.6.

7.1.1 Demographic Variables

Demographic variables, including date of birth, sex, height, weight, BMI (weight [kg]/height [m]²), race and smoking status will be collected at Screening.

7.1.2 Medical and Disease History

All active medical conditions and all surgeries will be recorded at Screening. Disease history, including date of diagnosis will also be recorded.

7.1.3 Reversibility Test

Reversibility in response to albuterol will be assessed at Screening as an eligibility measure. Spirometry (FEV₁ and FVC) assessment before and after four puffs (400 µg) of albuterol, administered using a pMDI, will be performed.

Three technically acceptable measurements should be made and recorded in the eCRF. Spirometry assessments may be performed up to eight times to obtain three acceptable readings according to ATS guidelines [Miller 2005]. The highest reading from each assessment will be used for calculation of predicted values and increase from baseline.

The following must be confirmed for inclusion:

- Post-bronchodilator FEV₁/FVC ratio of ≤ 0.70
- Post-bronchodilator FEV₁ $\geq 40\%$ and $\leq 80\%$ of predicted normal *
- Demonstrates ≥ 150 mL increase from pre-bronchodilator FEV₁

*National Health and Nutrition Examination Survey (NHANES) III [Hankinson 1999] will be used as a reference for normal predicted values.

7.1.4 Screening Laboratory Assessments, Chest X-ray

At Screening, blood samples will be taken and analyzed for viral serology (human immunodeficiency virus, hepatitis B and hepatitis C). A serum pregnancy test will be performed on women of childbearing potential. A FSH test will be performed, if required to confirm post-menopausal status. Regarding viral serology, patients who received a hepatitis B vaccination and are positive for hepatitis B surface antibody, but are negative for both hepatitis B surface antigen and hepatitis B core antibody, do not need to be excluded from the study. Samples will be taken and handled according to the laboratory manual and analyzed locally.

A chest X-ray (post-anterior) must be performed at Screening or in the 12 months prior to Screening.

7.1.5 Prior and Concomitant Medications and Therapies

Prior COPD therapies and medications will be recorded at Screening and concomitant use during the study recorded as described in Section [5.8.1](#).

Other prior medications will be separately recorded at Screening and concomitant use during the study recorded as described in Section [5.8.2](#).

7.1.6 Eligibility Check

Patients will be confirmed as eligible according to the Inclusion and Exclusion Criteria from assessments made at Screening with a final check of all results pre-dose in Part A.

7.2 Efficacy/Pharmacodynamic Assessments

7.2.1 Pulmonary Function Tests

Post-dose measurements will be taken in relation to the morning dose of RPL554 or placebo.

Spirometry assessments (FEV₁ and FVC) will be made in accordance with ATS/ERS guidelines [[Miller 2005](#)]. At all timepoints, three technically acceptable measurements will be made and recorded. Spirometry assessments may be performed up to eight times to obtain three acceptable readings. The highest FEV₁ and FVC readings from each assessment will be used for analysis even if the FEV₁ and FVC values come from two different forced exhalations.

7.2.2 Dyspnea Scale

Patients will be interviewed by a blinded member of study staff to assess their dyspnea. An 11-point Likert scale will be utilized, which will be anchored from 0 to 10 [[Davis 2006](#)]. The interview will be worded as follows: “On a scale from zero to ten, please rate your current shortness of breath, with zero indicating no shortness of breath and ten indicating the worst shortness of breath you can imagine.” This scale will be an instantaneous measurement of their dyspnea at that moment, and not reflective.

7.2.3 Rescue Medication

The use of rescue medication will be assessed as follows: 1) during study visits, by recording the amount of and time that rescue was taken, and 2) between Days 1 and 7 of each treatment period, by recording the weight of the canister.

7.3 Pharmacokinetic Assessments

Samples of 4 mL per time point will be collected by venipuncture or via indwelling cannula in the forearm into lithium heparin tubes and will be immediately chilled (ice bath). The blood will be centrifuged within 15 minutes of collection. The plasma will be separated in a refrigerated centrifuge (about 4°C) at 1100g for 15 minutes and transferred into polypropylene tubes. After each blood collection, the plasma will be dispensed into two aliquots. After appropriate labelling, the plasma samples will be stored at, or below -20°C. The primary plasma samples from both Part A and Part B will then be transported in dry ice to the external laboratory performing the

quantitative analysis of plasma RPL554 concentrations (LGC), where they will be stored at or below -20°C until they are submitted for analysis with a validated method.

RPL554 plasma metabolite analysis will be performed on a proportion of the back-up plasma samples corresponding to the patients receiving the highest dose of RPL554 in Part B. Further details of how these back-up samples will be selected will be provided in the bioanalytical protocol for the metabolite analysis. These plasma samples will be transported in dry ice to LGC, who will forward them to the external laboratory performing the plasma metabolite analysis (YBS/Unilabs) where they will be stored at or below -20°C until they are submitted for analysis. These data will be considered exploratory, will not form part of the study statistical analysis and will be reported separately in a bioanalytical report by YBS/Unilabs. The remaining back-up samples from Part A will be transported to LGC in a separate shipment from the primary plasma samples.

7.4 Safety Assessments

7.4.1 Adverse Events

7.4.1.1 *Adverse Event Definitions*

An adverse event is defined as any undesirable experience occurring to a patient, or worsening in a patient, during a clinical study, whether or not considered related to the study medication. An adverse event may be any of the following:

- A new illness
- An exacerbation of a sign or symptom of the underlying condition under treatment or of a concomitant illness
- Unrelated to participation in the clinical study or an effect of the study medication
- A combination of one or more of the above factors

No causal relationship with the study medication is implied by the use of the term “adverse event.” An exacerbation of a pre-existing condition or illness is defined as a more frequent occurrence or as an increase in the severity of the pre-existing condition or illness during the study. Planned or elective surgical or invasive procedures for pre-existing conditions that have not worsened are not adverse events. However, any complication that occurs during a planned or elective surgery is an adverse event (if the event fits the serious criteria, such as an extended hospitalization, it will be considered to be serious). Conditions leading to unplanned surgical procedures may be adverse events.

An adverse reaction is defined as all untoward and unintended responses to study medication related to any dose administered.

A serious adverse event (SAE) is any adverse experience that:

- Results in death
- Is life-threatening
- Requires inpatient hospitalization or prolongation of existing hospitalization
- Results in persistent or significant disability/incapacity, OR

- Is a congenital anomaly/birth defect
- Other medical events *

*Important medical events that may not be immediately life-threatening or result in death or hospitalization may be considered a SAE when, based on appropriate medical judgement, they may jeopardize the patient or may require medical or surgical intervention to prevent one of the outcomes listed above.

An unexpected adverse reaction is an adverse reaction in which the nature or severity of which is not consistent with the Investigator Brochure.

A suspected unexpected serious adverse reactions (SUSAR) is any suspected adverse reaction related to the study medication that is both unexpected and serious.

Standard procedures for emergency care should be followed for any individual adverse event, whenever clinically needed (decision to be taken by the Investigator).

7.4.1.2 Recording and Assessing Adverse Events

All adverse events, whether reported spontaneously by the patient, in response to open questioning on treatment days or observed by the Investigator or his/her staff, will be recorded from informed consent until the End of Study Visit. The start and stop time will be recorded and adverse events will be assessed by the Investigator for the following:

7.4.1.2.1 Severity

Mild:	Resolved without treatment
Moderate:	Resolved or was tolerated with specific treatment without affecting study activities
Severe:	Did not resolve or was not tolerated with treatment

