7.4.1.2.3 Causality

The Investigator will assess causal relationship between the study medication and each adverse event, and answer "yes" or "no" to the question, "Do you consider that there is a reasonable possibility that the event may have been caused by the study medication?"

For SAEs, causal relationship will also be assessed for study procedures, additional study medication, and other medication. Note that for SAEs that could be associated with any study procedure, the causal relationship is implied as "yes".

A guide to the interpretation of the causality question is found in Section [14.2](#).

7.4.1.2.4 *Action and Outcome*

- Action taken with study medication (none, study medication stopped, study medication temporarily interrupted)
- Other actions (none, concomitant medication, study discontinuation, hospitalization, other)
- The outcome and date of outcome according to the following definitions:
 - Recovered or resolved (adverse event disappeared)
 - Recovering or resolving (patient is recovering)
 - Not recovered or not resolved (adverse event remains without signs of improvement)
 - Recovered or resolved with sequelae (adverse event has resulted in permanent disability or incapacity)
 - Fatal
 - Unknown (only applicable if patient has been lost to follow-up)
- Seriousness (yes or no)

7.4.1.3 *Reporting Procedure for SAEs*

The Investigator must report all SAEs to the Sponsor as soon as practical, but in all cases within 24 hours of awareness. Any fatal SAEs notified in the 28-day period after the last dose of study drug must also be reported.

SUSARs will be determined by the Sponsor's Medical Monitor.

SAEs will be reported to the IRB and regulatory authority(ies) according to local requirements.

All adverse events will be followed until they have abated, or until a stable situation has been reached. Depending on the event, follow up may require additional tests or medical procedures as indicated, and/or referral to the patient's general physician or a medical specialist.

It is the responsibility of the Investigator to ensure that any necessary additional therapeutic measures and follow-up procedures are performed.

7.4.2 *Pregnancy*

In addition to the Screening serum pregnancy test (see Section 7.1.4), urine pregnancy tests will also be performed by the study center on women of childbearing potential at Screening (confirmed to be negative prior to the chest X-ray) and during the study.

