9.4.7 Safety

Safety data including laboratory safety tests, 12-lead ECG, vital signs and physical examinations, will be summarized by treatment group and timepoint of collection, when appropriate, for each of the two parts separately. For continuous variables, the change from baseline (pre-dose at each treatment period) to each post-dose time point will also be calculated and summarized. Data will further be illustrated by shift tables (showing changes from low/normal/high) and shift plots for selected time points. Separate listings will be generated of abnormal values occurring after the first dose of study treatment.

In Part A, change from baseline in peak pulse and peak heart rate will be compared between the treatments using analysis of covariance models with fixed factor treatment, and using the pre-dose baseline value as a covariate. In Part B, change from baseline in peak pulse will be compared between the treatments using analysis of covariance models with fixed factors for treatment, period and patient, and using the pre-dose Day 1 baseline value as a covariate. Additive model will be used for pulse and heart rate.

Coded adverse event terms will be presented by system organ class (SOC) and preferred term and summarized by treatment group for each part. Summary tables by treatment group with total number and number of patients with adverse events, SAEs, adverse events leading to discontinuation of study treatment, causally related adverse events and severe adverse events will be produced. Further SAEs, causally related adverse events and adverse events of each intensity will be summarized by SOC and preferred term.

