16.1.1. ALL TEAES

Incidence of TEAEs will be presented by System Organ Class (SOC) and Preferred Term (PT) and broken down further by maximum severity and relationship to study medication.

Document: Z:\RPL554\AZA40375\Biostatistics\Documentation\SAP\Verona RPL554-DP-201 SAP v1.0 – Part A

Author: [name]

Version Number: 1.0

Version Date: [19DEC2018]

Template No.: CS_TP_BS016 Revision 5

Reference: CS_WI_BS005

Effective Date: 01Apr2018

Copyright © 2009, 2010, 2012, 2016, 2018 IQVIA. All rights reserved. The contents of this document are confidential and proprietary to IQVIA Holdings Inc. and its subsidiaries. Unauthorized use, disclosure or reproduction is strictly prohibited.

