16.1.1.1. Severity

Severity is classed as mild/ moderate/ severe (increasing severity). TEAEs starting after the single dose of study medication with a missing severity will be classified as severe. If a patient reports a TEAE more than once within that SOC/ PT, the AE with the worst-case severity will be used in the corresponding severity summaries.

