16.1. ADVERSE EVENTS

Adverse Events (AEs) will be coded by MedDRA dictionary using the version specified in the data management plan.

Treatment emergent adverse events (TEAEs) are defined as AEs that started or worsened in severity on or after the first dose of study medication, based on the investigator assessment of severity. TEAEs will be assigned to treatment groups based on actual treatment received. TEAEs, like medications, may be assigned to multiple treatment groups due to the cross-over design of the study. This will depend on the occurrence date and duration of each TEAE.

See [Appendix 2](#) for handling of partial dates for AEs. In the case where it is not possible to define an AE as treatment emergent or not, the AE will be classified by the worst case; i.e. treatment emergent.

An overall summary of number of patients within each of the categories described in the sub-section below, will be provided as specified in the templates.

Listings will include TEAEs and Non-TEAEs.

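### Adverse event severity is graded mainly by resolution, treatment and tolerance, with overlaps and gaps, so the grades cannot support the planned intensity and maximum-severity tables

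*Protocol*

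**What the plan says.** Protocol 7.4.1.2.1 has three grades:

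- The lowest grade, Mild, is defined as "Resolved without treatment".
- The middle grade, Moderate, is defined as "Resolved or was tolerated with specific treatment without affecting study activities".
- The highest grade, Severe, is defined as "Did not resolve or was not tolerated with treatment".

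Other items already record much of this. Chronicity (Protocol 7.4.1.2.2) has a category for persistent events. Action and Outcome (Protocol 7.4.1.2.4) records concomitant medication as an action and, among the outcomes, "Not recovered or not resolved (adverse event remains without signs of improvement").

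The grades are then used as a scale of intensity. Protocol 9.4.7 says that "adverse events of each intensity will be summarized by SOC and preferred term", and also plans counts of severe events. Section 16.1.1 of both SAPs presents treatment-emergent events by system organ class and preferred term, "broken down further by maximum severity and relationship to study medication". Section 16.1.1.1 of both SAPs states "Severity is classed as mild/ moderate/ severe (increasing severity") without defining the grades, so the protocol's definitions apply. Section 16.1 of the Part B SAP counts an event as treatment emergent if it "started or worsened in severity on or after the first dose of study medication"; the Part A SAP has the same rule tied to the single dose.

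Protocol 4.3.1, on stopping study treatment, refers to intolerable or persistent events and adds that they may be of any severity.

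**The concern.** A severity table is read as showing how bad the events were. Here the grade mostly shows how the event ended and whether it was treated, so it largely repeats the outcome and action fields and leaves intensity unmeasured.

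That matters for this drug. Protocol 1.2 names headache, cough, dizziness and palpitations as the most common events with the nebulized suspension, and describes the heart-rate increases and the rise in dizziness as transient. If short, self-limiting events like these became more intense with dose but were left untreated, every one would still be graded Mild and the severity tables would show nothing. Safety and tolerability is a secondary objective in both parts, and Protocol 1.1 says this is the first clinical assessment of the dry powder formulation in humans.

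The grades also need to be reproducible. Where an event fits two grades or none, two investigators can grade it differently and both follow the protocol.

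**Working it through.** The plan gives no figure to reproduce, so the check is logical: apply the three definitions to every combination of four yes/no features and see which grades result.

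**Inputs.** T = treated, R = resolved, L = tolerated, S = study activities affected, giving 2 × 2 × 2 × 2 = 16 combinations.

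**Rules, from Protocol 7.4.1.2.1**

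- Mild: R and not T.
- Moderate: T, and (R or L), and not S.
- Severe, reading A (non-resolution counts whether or not the event was treated): not R, or (T and not L).
- Severe, reading B (the words about treatment qualify both halves of the sentence): T, and (not R or not L).

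Moderate is read as meeting either half, resolved or tolerated, with treatment and study activities as conditions on both.

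| T | R | L | S | Combinations | Reading A | Reading B |
|---|---|---|---|---|---|---|
| no | yes | any | any | 4 | Mild | Mild |
| no | no | any | any | 4 | Severe | none |
| yes | yes | yes | no | 1 | Moderate | Moderate |
| yes | yes | yes | yes | 1 | none | none |
| yes | yes | no | no | 1 | Moderate and Severe | Moderate and Severe |
| yes | yes | no | yes | 1 | Severe | Severe |
| yes | no | yes | no | 1 | Moderate and Severe | Moderate and Severe |
| yes | no | yes | yes | 1 | Severe | Severe |
| yes | no | no | any | 2 | Severe | Severe |

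**Totals**

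- Reading A: one grade in 4 + 4 + 1 + 1 + 1 + 2 = 13, two grades in 2, no grade in 1.
- Reading B: one grade in 4 + 1 + 1 + 1 + 2 = 9, two grades in 2, no grade in 4 + 1 = 5.

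These are counts of logical cases, not of events, and say nothing about how often each case occurs.

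**What follows under either reading**

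1. Every untreated event that resolves is Mild, whatever its intensity.
2. A treated, unresolved but tolerated event that leaves study activities undisturbed is both Moderate and Severe.
3. A treated, resolved and tolerated event that disturbs study activities has no grade. If the field were left blank, section 16.1.1.1 of both SAPs would count a treatment-emergent event of this kind as severe.

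**Worsening in severity.** Under these rules a grade changes only when treatment, tolerance, resolution or effect on study activities changes. An ongoing event that simply becomes more intense after dosing need not change grade, so the worsening clause can miss it.

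**Protocol 4.3.1 beside 7.4.1.2.1.** The first treats persistence and intolerability as separate from severity. The second uses non-resolution and lack of tolerance as the criteria for Severe. The two sections must be reconciled.

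**The case against.** The best defence is that the consequences are small. Adverse event tables are descriptive, and section 16 of the Part B SAP makes no treatment comparisons of safety data unless specified. Outcome, chronicity, action and seriousness are recorded separately, so a reader can separate duration from other features. The grades do have some functional content, through tolerance and effect on study activities. The treatment-emergence algorithm in Appendix 2 of both SAPs uses dates only, so the worsening clause is a secondary route. All of this stands and limits the importance of the point. It does not repair the overlaps and gaps, and recording duration elsewhere does not supply the missing intensity.

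A reader might go further and infer three things that the documents do not support:

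- *That severe counts would measure length of follow-up, with last-period events having only the 4 to 10 days before the End of Study Visit to resolve.* Protocol 7.4.1.3 follows all events until they abate or stabilize and sets no cut-off at that visit. In the ten sequences in Appendix 1 of the Part B SAP each treatment is last exactly twice: placebo in 1 and 7, 150 µg in 5 and 10, 500 µg in 6 and 8, 1500 µg in 2 and 3, 3000 µg in 4 and 9. Apart from dropout or unequal sequence sizes, a last-period effect would not favor one treatment.
- *That every unresolved event must be Severe.* An untreated one is Severe only under reading A, and a treated, tolerated one that leaves study activities undisturbed also fits Moderate.
- *That a given percentage of events would move grade.* Any such figure would only restate its own assumption.

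**Conclusion.** The point stands as a defect of definition. The grades are based mainly on resolution, treatment and tolerance, with a limited functional element, and they are neither mutually exclusive nor exhaustive under either reading of Severe. They do not support tables by intensity, the maximum-severity tables, or the worsening part of the treatment-emergence definition, and they do not fit Protocol 4.3.1.

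Misgrading affects events whose intensity and course differ; how many there would be cannot be estimated from the documents. The effect is on descriptive safety outputs only; the efficacy and pharmacokinetic analyses are untouched. The conclusion assumes that sites grade by the protocol wording as written, since neither SAP offers another definition.

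**What to change.** Replace the three definitions in Protocol 7.4.1.2.1 with mutually exclusive, exhaustive grades based on intensity, for example on interference with usual activities. Leave resolution, treatment and persistence to the existing Outcome, Action and Chronicity items. Repeat the definition in section 16.1.1.1 of the SAP, and reconcile the wording with Protocol 4.3.1.

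Where grades have already been collected under the current wording, keep them. Put that definition in the table titles or footnotes, do not present the grades as intensity, and state which scale applies to an event that spans Parts A and B. The last item is needed because the same patients enter both parts and Protocol 7.4.1.2 records events from consent to the End of Study Visit.

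The cost is a small further amendment and a change to CRF guidance. It cannot be assumed to ride on the amendment that set the Part B doses: the Part B SAP of 08JUL2019 already rests on protocol version 2.0 of 12FEB2019. The two parts may end up on different scales, which is tolerable because Protocol 9.4.7 summarizes them separately. If it is too late to change collection, honest labelling alone costs only table text.
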